1.2. Objectives

1.2.1. Primary Objective

To determine the safety and tolerability in subjects who receive FF-10501-01 for the treatment of advanced hematologic malignancies.

1.2.2. Secondary Objective

- To determine the overall response rates
- To evaluate the proportion of subjects who achieve hematologic improvement in peripheral blood or bone marrow blast count
- To evaluate progression-free survival (PFS)

- To evaluate overall survival (OS)
- To evaluate the pharmacokinetics of FF-10501 and M1
- To evaluate xanthosine monophosphate (XMP) as a pharmacodynamic marker

1.3. Treatment(s)

1.3.1. Treatment Assignments

Phase 1:

14-day Schedule: Following Screening, a total of 6 cohorts of 3 subjects each received oral doses of 50, 100, 200, 300, 400 or 500 mg/m² BID per day (100, 200, 400, 600, 800 or 1000 mg/m²/day) for 14 days, followed by 14 days off, repeated every 28 days (= 1 cycle). Three events of drug-related atrial fibrillation (Grade 2) were reported in 2 subjects at a dose of 500 mg/m² BID (Cohort 6). Study drug was suspended in both subjects and all events resolved with oral metoprolol treatment. These events were medically important events and thus met the definition of dose-limiting toxicity (DLT). No further enrollment was made at this dose level. The maximally tolerated dose (MTD) was declared at 1 dose level below the dose eliciting DLT, 400 mg/m² BID, and this cohort was expanded to 6 subjects. No DLTs were observed in N=7 total subjects treated at 400 mg/m² BID x 14 days.

21-day Schedule: At the MTD of 400 mg/m² BID, Cohort 7 was added to extend the BID dosing schedule to 21 days followed by 7 days off, repeated every 28 days (=1 cycle).

28-day Schedule: At the MTD of 400 mg/m² BID, Cohort 8 is added to extend the BID dosing schedule to 28 days continuous dosing each 28 days (=1 cycle).

DLT is defined as Grade 4 hematologic toxicity lasting 7 days or more; Grade 3 nonhematologic toxicity of any duration not amenable to supportive care; failure of platelets, absolute neutrophil count (ANC), or hemoglobin (Hb) to recover to Grade 1 within 12 weeks despite use of platelet and red blood cell (RBC) transfusions and/or growth factors; febrile neutropenia (defined as ANC<1000/mm³ with a single temperature of > 38.3°C or sustained temperature of ≥ 38°C for over one hour); Grade 3 thrombocytopenia associated with bleeding; or other important medical event.

At the MTD of 400 mg/m² BID, the 28-day continuous schedule of administration resulted in a higher rate of adverse events with no additional efficacy versus the 21-day schedule. Therefore, the recommended Phase 2 dose (RP2D) and schedule was determined to be 400 mg/m² BID on a 21-day schedule of administration, repeated every 28 days.

Phase 2a: Once 6 subjects are treated at the RP2D and schedule in Phase 1, 1 additional cohort will enroll 20 subjects with MDS/CML who have relapsed from, or are refractory to, prior hypomethylating agent (HMA) therapy. Subjects enrolled in Phase 1 at the RP2D and schedule and who meet the Phase 2a selection criteria will count towards the Phase 2a accrual. Dose level adjustments for adverse events will be made.

1.3.2. Selection and Timing of Doses

For all subject cohorts, if 1 of 3 subjects per cohort experiences DLT, the cohort will be expanded to 6. If 2 of 6 subjects per cohort experience DLT, all further dose escalation will

stop. If 0 of 3 or \leq 1 of 6 subjects per cohort experience DLT by Day 28 following dosing of FF-10501-01, dose escalation will proceed to the next cohort. At the MTD of 400 mg/m² BID, the longest schedule of administration below the schedule of administration eliciting DLT will be declared the recommended Phase 2 dose (RP2D) and schedule. A total of 6 subjects will be treated at the RP2D and schedule. No intra-subject dose escalation will be allowed from previous dose levels/schedules of administration until at least one subject has completed Cycle 1 at the longer schedule of administration (e.g., 21 or 28 days) with no Grade 2 or greater toxicities observed. Additionally, patients currently on study will have the option to extend their current dosing schedule to 21 days, followed by 7 days off, repeated every 28 days (=1 cycle), or 28 days of continuous dosing, whichever is chosen as the best schedule, if seen in the patient's best interest by the principal investigator. Dose level adjustments for DLT will be made. Subjects who experience DLT at the first dose level, 50 mg/m² BID, will not be dose-reduced. Up to 48 subjects are planned for Phase 1.

Subjects on the 21-day schedule will receive FF-10501-01 on a BID schedule. For all subjects on the 21-day dosing schedules, blood samples for pharmacokinetic assessment of FF-10501 and M1 in plasma will be collected on Cycle 1 Day 1 pre-dose (any time), between 0.5-1 hr post-dose, and between 2-4 hr post-dose, and Day 15 pre-dose (within 15 minutes prior to dosing), between 0.5-1 hr post-dose, and between 2-4 hr post-dose.

Subjects who demonstrate objective response (OR) or stable disease (SD) will be allowed to continue therapy with FF-10501-01 until progression of disease, observation of unacceptable adverse events, intercurrent illness or changes in the subject's condition that prevents further study participation.

1.4. Procedures

1.4.1. Subject Identification

Once study eligibility has been determined, a subject will be enrolled into the study and will be assigned a sequential Subject Identification number within each participating site. The identification number will consist of a 2-digit site number, 1-digit cohort number, and a 2 digit subject number. The subject identification number will be assigned sequentially within the cohort. The cohort number will remain the same if a subject's dose is increased or decreased. If a subject is replaced, the identification number will not be reassigned.

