3.4.2. Adverse Events

All safety endpoints will be summarized using descriptive statistics and will be by dose cohort for phase 1 subjects and by MDS/CMMML disease cohort for phase 2a subjects treated at RP2D and schedule using the FAS population.

All AEs will be coded based on the Medical Dictionary for Regulatory Affairs (MedDRA; Version 17.0 or higher). An AE will be considered a treatment emergent adverse event (TEAE) if the onset is after the first dose of study drug or if the condition was present at baseline but worsened after the first dose. All other AEs will be considered preexisting events.

All AEs for each subject will be listed, including Treatment Emergent status, intensity grading, relationship to study drug, action taken and outcome. Subject listings of deaths, serious TEAEs, and TEAEs leading to treatment discontinuation will be provided. Summary tables will be prepared to examine TEAE severity and relationship to study treatment.

TEAE summaries will be produced separately for each dose cohort for subjects in Phase 1 and by MDS/CMMML disease cohort for subjects in Phase 2a. All TEAE summaries will show the number and percentage of subjects experiencing at least 1 TEAE for each preferred term, arranged by system organ class, and the number of unique occurrences of the event. Separate summaries will be produced by relationship to study medication, and by severity, and for those events with an incidence of at least 2% in any group or overall. Subjects with multiple events will be counted only once per SOC and preferred term. For each level of summarization, the event with the highest level of severity, grade, or strongest drug relationship will be presented. TEAEs with Grade 3 or Grade 4 and drug-related TEAEs with Grade 3 or Grade 4 will be summarized. TEAEs leading to study drug interruption or discontinuation, Grade 3 and 4 TEAEs, Serious TEAEs will be provided in a separate listing.

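### Phase 1 adverse events that follow a dose or schedule increase are tabulated only under the starting cohort; no planned summary shows the regimen at onset

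*SAP*

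**What the plan says.** **Increases are permitted.** SAP 1.3.2, repeated in Protocol 3.1, sets a condition and then leaves the way open: "No intra-subject dose escalation will be allowed from previous dose levels/schedules of administration until at least one subject has completed Cycle 1". The cycle in question must be on the longer schedule, with 21 and 28 days named as examples, and must have passed without toxicity of Grade 2 or above. No limit on the size of the step is given. Separately, "patients currently on study will have the option to extend their current dosing schedule to 21 days"; continuous 28-day dosing is the alternative, and which of the two applies depends on the schedule judged best. SAP 1.3.1 records the choice that was made: the "schedule was determined to be 400 mg/m² BID on a 21-day schedule of administration, repeated every 28 days".

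**The label is fixed.** SAP 1.4.1 builds the subject identifier from site, cohort and subject digits. It then adds a rule that opens "The cohort number will remain the same if"; the case that the rule goes on to name is a rise or fall in dose, and a change of schedule is not mentioned.

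**The tables use the cohort.** SAP 3.4.2: "TEAE summaries will be produced separately for each dose cohort for subjects in Phase 1". SAP 3.4.1 and 3.4.3 to 3.4.5 group Phase 1 exposure, laboratory, vital-sign and ECG summaries in the same way, and SAP 4.1 sets dose cohort as the grouping for all Phase 1 tables. Phase 2a tables are by disease cohort. A TEAE is any event that starts or worsens after the first dose, with no cut-off at a change of regimen.

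**The concern.** Taken together, these rules count an event that occurs after an increase in the column of a regimen the subject was no longer taking. The lower-dose or shorter-schedule column can gain events that it did not produce, and what switchers experienced at the higher regimen appears in no summary.

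The primary objective is safety and tolerability, and SAP 2.4.2 plans no formal hypothesis tests, so the descriptive tables are the safety analysis. Most cohorts began with 3 subjects, and single events shape the pattern. Protocol 1.7.2 reports drug-related Grade 3 or 4 events in one patient at 200 mg/m² BID and one at 300 mg/m² BID among 33 treated to date. The choice of schedule in SAP 1.3.1 itself rested on comparing adverse event rates between the 28-day and 21-day regimens, yet no planned table would place a switcher's events under either.

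**Working it through.** **1. The plan's own figures.** Daily dose = 2 x BID dose. For 50, 100, 200, 300, 400 and 500 mg/m² this gives 100, 200, 400, 600, 800 and 1000 mg/m²/day, as SAP 1.3.1 states. The documents give no per-cycle dose.

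**2. Per-cycle dose** = 2 x BID dose x dosing days in the 28-day cycle.

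- 50 mg/m² BID x 14 days: 2 x 50 x 14 = 1,400 mg/m²
- 400 mg/m² BID x 21 days: 2 x 400 x 21 = 16,800 mg/m²; 16,800 / 1,400 = 12
- 400 mg/m² BID x 28 days: 2 x 400 x 28 = 22,400 mg/m²; 22,400 / 1,400 = 16

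Ratio of per-cycle dose after a move to 400 mg/m² BID, by starting level on the 14-day schedule:

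| Starting dose (mg/m² BID) | Per cycle at start (mg/m²) | To 400 x 21 days | To 400 x 28 days |
|---|---|---|---|
| 50 | 1,400 | 12 | 16 |
| 100 | 2,800 | 6 | 8 |
| 200 | 5,600 | 3 | 4 |
| 300 | 8,400 | 2 | 2.67 |
| 400 | 11,200 | 1.5 | 2 |

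Schedule extension at an unchanged dose gives 21/14 = 1.5 or 28/14 = 2 at every level.

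**3. Tablet rounding.** Protocol Appendix A gives 100 mg per dose at the 50 mg/m² level up to a body surface area of 2.00 m², and 500 to 900 mg at the 400 mg/m² level. For 1.25 to 2.2 m² the delivered ratio for the largest move is 7.5 to 12 (21 days) or 10 to 16 (28 days). The low end is (500/100) x 1.5 = 7.5. The maximum is reached at 1.92 to 2.00 m²: (800/100) x 1.5 = 12.

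**4. Weight of one event.** One post-increase event in a cohort with none before it moves the rate from 0/3 to 1/3 (33%), or from 0/6 to 1/6 (17%).

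**5. Does the exposure table repair this?** SAP 3.4.1 divides total dose by scheduled days on drug, and then by starting dose. A subject moved from 50 to 400 mg/m² BID for most cycles could approach 400/50 = 8 (800%). A subject who only extends the schedule stays near 1, because the scheduled days rise with the dose. The table would flag some increases and miss others, and it places no event under a regimen.

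**6. Does the fixed identifier define the table column?** SAP 1.4.1 is a numbering rule, and no separate definition of dose cohort appears in the text I had. SAP 2.1 counts up to 8 dose cohorts of 3 to 6 subjects (8 x 6 = 48, as stated), which takes in the 21-day and 28-day Cohorts 7 and 8. So the term appears to mean the numbered cohort.

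**The case against.** The other side has several good points.

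- **A reader might infer that the RP2D is made to look less toxic.** The documents do not support this. A subject who starts lower and later moves up is absent from both numerator and denominator of the RP2D columns. Switchers are also selected for having stayed on treatment, so including them could lower that rate as easily as raise it. What is lost is information; the direction is unknown.
- **A reader might take 12-fold or 16-fold as something that happened.** No document reports any switch. The responder at 50 mg/m² BID followed for at least 28 cycles (Protocol 1.7.2) shows only that there was time for one; median treatment was 2 cycles. The ceiling needs a full dose increase plus a longer schedule. The 28-day figure rests on the parenthesis in the escalation clause, whereas the extension option follows the schedule judged best, and 21 days was selected.
- **A reader might conclude that dose-finding was compromised.** It was not. Escalation uses DLTs by Day 28, at the assigned regimen.
- **Scope.** Phase 2a tables are by disease cohort, so the point concerns Phase 1. The sentence in SAP 1.4.1 names dose, not schedule.
- **Reconstruction is possible.** SAP 4.3 lists diaries, dispensation, TEAEs and events leading to dose adjustment, and the cohorts are small.

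The last point softens the concern without removing it: the reader of the tables would have to do the reconstruction by hand, and no planned listing is designed to identify increases.

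**Conclusion.** The point stands as a gap in the Phase 1 safety plan, and it is a cheap one to close. If any subject's dose or schedule was increased, later events are charged to the starting cohort. That can inflate toxicity in lower-dose or shorter-schedule columns and omits switchers' experience at the higher regimen. The difference in per-cycle dose is 1.5-fold or 2-fold for schedule extension alone, with a theoretical ceiling of 12-fold (21 days) or 16-fold (28 days).

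This rests on three assumptions: that dose cohort in the tables means the fixed cohort number; that the number also stays fixed after a schedule change; and that at least one subject was switched, which the documents leave open. One SAP section, between 2.4.4 and 2.4.6, was not in the text I had and cannot be judged.

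**What to change.** Keep the identifier rule and the full TEAE tables by assigned cohort. Cutting those tables off at the first increase would conflict with the SAP's own TEAE definition.

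In SAP 3.4.2 and 4.1.6.2 add, for Phase 1:

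1. A table of TEAEs and of Grade 3 or higher TEAEs by actual dose and schedule at onset, with subject-cycles as denominator. State the rule for allocation, for example that an event in the off-drug days belongs to the regimen of that cycle. The same table would correctly place events after dose reductions.
2. A listing of subjects whose dose or schedule was increased, with the old and new regimen and the date of change.
3. Optionally, as a sensitivity display, a by-cohort table limited to events before the first increase.

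It would also help to define dose cohort once in the SAP and to say that it does not change with schedule, if that is meant.

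The cost is a little programming from dosing data that are already collected. A subject can appear in more than one column, and switchers are a selected group who stayed on treatment, so the added table is descriptive and should carry a footnote saying so.

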1.4.2. Randomization

Not Applicable

1.4.3. Blinding/Unblinding

This is an unblinded study.

1.4.4. Replacement

Subjects who are enrolled and are assigned a Subject Identification number but do not receive FF-10501-01 will be replaced.

1.4.5. Data Monitoring

During the study, a Safety Review Committee, consisting of the actively recruiting investigators, the Medical Monitor, and FUJIFILM Pharmaceuticals (FPHU), will review data from each cohort on an ongoing basis.

The Sponsor is responsible for ensuring the proper conduct of the study with regard to ethics, protocol adherence, site procedures, integrity of the data, and applicable laws and/or regulations. At regular intervals during the study and following completion of the study, the sponsor's study monitors will contact the study site via visits to the site, telephone calls, and letters in order to review study progress, CRF completion, and address any concerns or questions regarding the study conduct. During monitoring visits, the following aspects of study conduct will be carefully reviewed: informed consent of subjects, subject recruitment, subject compliance with the study procedures, source data verification, drug accountability, use of concomitant therapy by subjects, AE and SAE documentation and reporting, and quality of data. Records pertaining to these aspects are expected to be kept current.

2. Statistical Analysis Considerations

2.1. Sample Size and Power

Up to 68 total subjects are planned in this study.

Phase 1: Up to 48 subjects are planned for Phase 1. The sample size reflects requirements associated with a 3+3 design. A total of 3 to 48 subjects are planned (3 to 6 subjects in up to 8 dose cohorts).

Phase 2a: The sample size reflects an additional 20 patients to be treated at the RP2D and schedule with CMML/MDS.

2.2. Analysis Populations

2.2.1. Full Analysis Set (FAS) Population

The full analysis set (FAS) includes all subjects who are administered any fraction of a dose of study medication

2.2.2. Randomized Population

Since this is not a randomized study, there is no randomized population.

2.2.3. Per Protocol Set (PPS) Population

For a particular measure, the per protocol set (PPS) includes those subjects in the FAS who have a valid baseline and one or more post-treatment assessments for that measure of interest.

2.2.4. Safety Population

All safety endpoints will be based on the FAS dataset.

2.2.5. PK/PD Population

The FF-10501-1 PK population consists of all subjects in the FAS who complete at least one post-dose PK assessment. The PD population consists of all subjects in the FAS who complete at least one post-dose PD assessment.

2.3. Data Handling

2.3.1. Measurement Times

2.3.1.1. Visit Windows

Visit windows will not be used. The visit time point entered on the case report forms will be used. Unscheduled assessments, if any, will be listed, but will not be included in tabulations by visit.

2.3.1.2. Baseline Values

The screening assessments are performed within 28 days of Cycle 1, Day 1, before the first dose of study medication. Unless otherwise mentioned, baseline will be the last observation before patients receive initially assigned dose. Generally, this will be Cycle 1 Day 1 pre-dose measurements. If a pre-dose assessment is not performed on Cycle 1 Day 1, the immediate previous non-missing value, including screening, will be treated as baseline. If there are multiple baseline assessments, the most recent one will be flagged as the baseline value and will be used for statistical analysis (evaluations may occur on the same day as Study Day 1, prior to dosing).

2.3.2. Missing Data Conventions

Unless otherwise specified, missing data will be considered missing and will not be imputed.

2.3.3. Imputation of Incomplete Dates

Imputation of partial dates may be performed during the data analysis and will be documented. For start date of Adverse Event (AE) or Concomitant Medication (CM) with a missing day, the imputed date is the first day of the month. For stop date of AE or CM with a missing day, the imputed date is the last day of the month. For start date with both missing day and missing month, the imputed date is the subject start study date if AE or CM start year is the same as study start year. Otherwise, the imputed start date is the first day of the year. For stop date with both missing day and missing month, the imputed date is the subject end of study date if AE or CM stop year is the same as the study end year. Otherwise, the imputed stop date is the last day of the year.

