7.1.4. Adverse Event Reporting Period

The adverse event reporting period begins from the date of the first dose of study drug to 28 days following the last dose of study drug.

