7.1.5. Recording of Adverse Events

Each AE should be recorded in standard medical terminology on the AE CRF module. Whenever possible, the AE should be evaluated and reported as a diagnosis rather than as individual signs or symptoms. For example, cough, runny nose, sneezing, sore throat, and head congestion should be reported as 'upper respiratory infection'. If a definitive diagnosis is not possible, the individual signs and symptoms should be recorded. Dates of

start (onset) and stop (recovery), action taken, and outcome will be recorded in the AE CRF module.

All clinically significant abnormal changes in laboratory parameters will be recorded as an AE on the AE module, with the following exceptions: clinically significant abnormal laboratory changes determined to be related to the study condition and concomitant conditions, e.g., diabetes, of which the investigator was previously aware and that have not worsened.

The investigator will evaluate all AEs with regard to maximum intensity and relationship to study drug, as follows.

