4.1.6.2. Adverse Events Summaries

- Summary of Treatment Emergent Adverse Events

- Treatment Emergent Adverse Events by System Organ Class and Preferred Term
- Treatment Emergent Adverse Events by Relationship to Study Drug
- Summary of Treatment Emergent Adverse Events by Severity
- Grade 3 and Grade 4 Treatment Emergent Adverse Events
- Drug-related Grade 3 and Grade 4 Treatment Emergent Adverse Events
- Treatment Emergent Adverse Events by System Organ Class and Preferred Term with at least 2% Incidence in any Group or overall

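### A new adverse event with a missing onset day in the month of first dose is imputed to the 1st of that month, so it cannot count as treatment-emergent

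*SAP*

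**What the plan says.** SAP 2.3.3 allows partial dates to be imputed. For the start date of an "Adverse Event (AE) or Concomitant Medication (CM) with a missing day, the imputed date is the first day of the month". The month of first dose is not an exception. When day and month are both missing there is an anchor: "the imputed date is the subject start study date if AE or CM start year is the same as study start year". The SAP does not say which date that is.

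SAP 3.4.2 then classifies events: "An AE will be considered a treatment emergent adverse event (TEAE) if the onset is after the first dose of study drug", or if a condition present at baseline worsened after it. It adds: "All other AEs will be considered preexisting events". The incidence tables in SAP 4.1.6.2, such as "Treatment Emergent Adverse Events by System Organ Class and Preferred Term", are tables of TEAEs. On counting, SAP 3.4.2 says: "Subjects with multiple events will be counted only once per SOC and preferred term".

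Protocol 7.1.4 fixes when events are collected: "The adverse event reporting period begins from the date of the first dose of study drug to 28 days following the last dose". Protocol 7.1.5 requires dates, not times: the dates of "start (onset) and stop (recovery), action taken, and outcome will be recorded in the AE CRF module".

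**The concern.** The 1st of a month is never later than a first-dose date in that month. Take a subject first dosed on 15 March with a new event on 20 March, recorded as March with the day missing. The imputed onset is 1 March, so the event is classed as preexisting, although the protocol's reporting period had not begun on 1 March. The worsened-at-baseline clause does not help, because the event is new.

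Safety and tolerability is the primary objective, and the TEAE tables are its main numerical output. For new on-treatment events the error runs one way: it can only remove events, and mostly those soon after the start of dosing. The cohorts are small, so one lost subject is visible in a percentage. The serious-event and discontinuation listings in SAP 4.3 are also restricted to TEAEs, so such an event could be missing there too.

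**Working it through.** The plan states no figure to reproduce. The check applies its two rules literally to calendar dates.

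**Inputs**
- Imputed onset = 1st of the true onset month (SAP 2.3.3).
- Treatment-emergent if imputed onset is later than the first-dose date (SAP 3.4.2, compared on dates because the CRF records dates).
- Assumptions: every first-dose date in a four-year calendar cycle is equally likely (1,461 days, 48 months); Day 1 is the first-dose date; true onset is uniform over Days 2–28.

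**Within the first-dose month**
- Of 365 possible first-dose dates, the imputed date is earlier for 353, equal for 12 (dosing on the 1st) and later for 0. In a leap year the counts are 354, 12 and 0 of 366.
- Taking every pair of first-dose date and later onset in the same month, 0 of 5,373 pairs are classed as TEAEs (0 of 5,401 in a leap year).

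**Across Days 2–28**

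An onset *k* days after first dose falls in the same month for *L* − *k* of the *L* first-dose dates in a month of length *L*. For *k* from 1 to 27, summing over 48 months gives:

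- share failing the test (imputed date on or before first dose) = (1461 − 48*k*)/1461 = 1 − 48*k*/1461
- share dated strictly before first dose, which leaves out dosing on the 1st = 1 − 48(*k* + 1)/1461

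Both are linear in *k*, so the mean over a period uses the mean *k*.

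| True onset | Mean *k* | Dated before first dose | Fails the test |
|---|---|---|---|
| Days 2–8 | 4 | 1 − 240/1461 = 0.836 | 1 − 192/1461 = 0.869 |
| Days 9–15 | 11 | 1 − 576/1461 = 0.606 | 1 − 528/1461 = 0.639 |
| Days 16–22 | 18 | 1 − 912/1461 = 0.376 | 1 − 864/1461 = 0.409 |
| Days 23–28 | 24.5 | 1 − 1224/1461 = 0.162 | 1 − 1176/1461 = 0.195 |
| Days 2–28 | 14 | 1 − 720/1461 = 0.507 | 1 − 672/1461 = 0.540 |

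Given onset in the first-dose month, the share dated strictly before first dose is 741/789 = 0.939. The share failing the test is 100%.

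**Effect of one lost subject on an incidence:** 1/3 = 33.3 points, 1/6 = 16.7, 1/7 = 14.3, and 1/20 = 5.0 in a pooled Phase 2a cohort.

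**Does a floor alone repair it?** If the imputed onset is the later of the 1st and the first-dose date, it equals the first-dose date. Under strict *after*, compared on dates, 0 of 5,373 pairs are still TEAEs. With *on or after*, all 5,373 are (5,401 of 5,401 in a leap year). Both changes are needed.

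**The case against.** The strongest reply concerns size. Cycle 1 has visits on Days 8, 15 and 22 and at the end of the cycle, each with an AE assessment. Onset dates are required on the CRF and monitors verify source data. Missing onset days may therefore be rare, above all in the first two weeks, where the shares above are highest. This stands: the documents give no count of partial dates, so the percentages are shares of missing-day events and not of all events. The 14 to 33 points also arise only if the subject has no other qualifying event of that term.

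Imputation is also optional under SAP 2.3.3. That makes the effect conditional, but the available SAP text gives no other way to classify an event without a full onset date, so not imputing leaves a gap.

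*After the first dose* can be read by clock time. An event later on Day 1 would then qualify, and the 100% and 54% figures depend on comparing dates. The 94% and 51% do not, since those events are dated to an earlier day. The *on or after* wording is best seen as a consequence of the floor.

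Finally, SAP 3.4.2 promises a listing of all events with their treatment-emergent status, and DLTs and deaths have their own listings. A misclassified event could be found there, but the listings do not correct the incidence tables.

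**Conclusion.** The rule as written gives a wrong result in one direction. When it is applied, no new event with a missing onset day in the first-dose month can enter the TEAE tables on a date comparison, and about 94% of such events are dated before treatment began. Over Days 2–28, 51% of missing-day events are dated before first dose and 54% fail the test, assuming uniform onset and a random calendar start. The absolute effect cannot be estimated without the number of partial dates and may be small. The point should still be corrected, because it bears on the primary objective, the cohorts are small and nothing in the available text offsets it.

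**What to change.** **SAP 2.3.3:** when the known month and year of AE onset (or the year, if the month is also missing) equal those of first dose, impute the first-dose date, unless the stop date shows that the event ended before first dose. Otherwise use the first of the month or year. For AEs, name the first-dose date in place of the undefined study start date.

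**SAP 3.4.2:** define a TEAE as an event with onset on or after the date of first dose, or a baseline condition that worsened after it.

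The cost is two SAP sentences and a small programming change. TEAE counts may rise slightly. A true pre-dose event recorded in the first-dose month, with no stop date before first dose, would count as a TEAE, as would a new event on Day 1 before the dose. For a safety objective that is the conservative direction.
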